1 PROTOCOL SUMMARY

1.1 SYNOPSIS

Title:	Dance – Randomized Controlled Trial
Study Description:	This project aims to enhance self-compassion in adolescent dancers recovering from a foot and ankle injury by incorporating the use of a mental health intervention app using gamified design during their recovery.
Objectives:	Primary Objective: To assess rates of return to dance without limitations after start of non-operative treatment in dancers recovering from foot and ankle injuries Secondary Objectives: 1) To assess self-compassion in the recovering dancer during and after the nonoperative treatment of their foot and ankle injury 2) To assess musculoskeletal function during and after the recovery process
Endpoints:	Primary Endpoint: Return to dance after treatment of injury Secondary Endpoints: 1) Self Compassion (SCS) scores collected at 3, 6, 12, 18, and 24 months 2) Foot and Ankle Ability Measure (FAAM) and Patient-Reported Outcome Measurement Information System (PROMIS)
Study Population:	13-18 year old dancers
Phase:	Not applicable – not a drug trial
Description of Sites/Facilities Enrolling Participants:	Rady Children's Hospital, San Diego
Description of Study Intervention:	Qualifying participants will all be placed in a physical therapy recovery program for their injury and randomized into treatment or control group for implementation of the gamification mental health app to use during their recovery path. Outcomes scores for pain, physical function and emotional distress will be collected at the time of enrollment, 3 months, 6 months, 12 months, 18 months and 24 months after the start of treatment.
Study Duration:	4 years
Participant Duration:	2 years

1.2 SCHEMA

1.3 SCHEDULE OF ACTIVITIES (SOA)

Procedures	W	C	L	O	8	≥	Φ	3	E	o	ω	E	o	–	>	Φ	–	∞	E	2	>	Φ	
Informed consent	X																						
Demographic s	X																						
Medical History	X																						
Randomizati on	X																						
Physical Exam	X		X		X		X		X		X		X		X		X		X		X		
Outcomes Scores	X			X		X		X		X		X		X		X		X		X		X	
Standard PT activities	X		X		X*																		
App intervention (treatment group only)	X		X		X																		

*= Additional PT up to 12 weeks/3months may or may not be ordered by the treating physician for both the treatment group and observation group depending on the recovery of the subject's foot and/or ankle injury

2 INTRODUCTION

2.1 STUDY RATIONALE

A dance injury can create psychological distress (11). We aim to explore the effect on return to dance, recurrence of injury and mental health during and after treatment of dance injury via the use of a mental health intervention. Low self-compassion specifically has been linked to psychological distress in athletes which can impair the recovery process during injury (21). This is an unexplored area in the dance population, which we aim to examine through this study. The gamified mental health app SuperBetter has been shown to have a positive and comparable effect on anxiety and depression scores when compared with group Cognitive Behavioral Therapy (CBT) interventions (5). We do not currently have the resources to administer group CBT interventions and therefore are using the gamified app as a proxy. It has also been shown to be an effective intervention with improved outcomes in treatment of adolescent concussion patients (1). Its use has not been explored in adolescent athletes. Thus, this project aims to enhance self-compassion in adolescent dancers recovering from a non-operative foot

and ankle injury by using a gamification mental health app to augment the physical therapy and home exercise program during the recovery course.

2.2 BACKGROUND

There is a noticeable disparity in the amount of research focusing on mental health and injury prevention in athletics versus dance, particularly when it comes to available interventions for use during the recovery process. In athletics, numerous studies examine mental health issues like depression and anxiety, with well-developed injury prevention strategies. These studies often feature well-designed, prospective research. In contrast, dance-related studies on mental health are fewer, with a lack of applied interventions, and a predominant focus on young adult dancers. Injury prevention in dance is less explored, with some studies highlighting risk factors but calling for more research on mental and preventive strategies. Overall, athletics outside of dance has a more extensive body of research, while dance still needs more comprehensive studies, particularly in the application of mental health interventions. The SuperBetter app was created by Jane McGonigal to address psychological symptoms that affected her during recovery from a serious concussion (23). A study in 2021 looked at the efficacy of app usage for mental health and demonstrated efficacy in improving anxiety and depression for the SuperBetter app (22). We plan to use it as a proxy to traditional CBT and explore the association between direct mental health intervention and the indirect effect on self-compassion during injury recovery in this study.

2.3 RISK/BENEFIT ASSESSMENT

2.3.1 KNOWN POTENTIAL RISKS

Use of the gamification app requires use of an electronic device which could increase screen time use in developing adolescents. The use of the app would be limited to no more than 15 minutes daily and would be discussed with guardians prior to implementation. Patients who do not have access to a smart phone or tablet may not be able to participate in the study. Patients may experience boredom or fatigue with the app and/or study questionnaires. Though unlikely, subjects may experience emotional discomfort or distress from the content of the app and/or study questionnaires. While the questionnaires do not ask about specific, potentially traumatic experiences, broadly being asked about feelings such as depression and compassion for oneself may feel uncomfortable for some. To avoid this risk, we will verbalize during enrollment that subjects may skip any questions they wish should any make them feel uncomfortable. The only additional risk to participants involved in the trial is potential loss of confidentiality. All measures to ensure patient confidentiality will be employed, including password protection of research files and devices, locked access to the research cabinet, coding of data with separate storage of the key and coded data, and restricted access limited to those who have a need to know for performance of their responsibilities.

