6 STUDY INTERVENTION

6.1 STUDY INTERVENTION(S) ADMINISTRATION

6.1.1 STUDY INTERVENTION DESCRIPTION

The study intervention will be mental health exercises via the SuperBetter app for dancers participating in PT rehab for foot or ankle injuries. The control will be PT rehab only, without implementation of the SuperBetter app.

Subjects who enroll and are randomized into the treatment arm will be assisted in clinic to log into the app SuperBetter. They will be added to the group run by the “host”/study staff. The SuperBetter app offers a daily exercise on a schedule that will be managed by the “host” or study staff. Subject will complete 1 full activity per day. This activity will not exceed 15 minutes in total including app boot-up, but the full activity itself will not exceed 10. These activities ask participants to practice different exercises that might be found in Cognitive Behavioral Therapy, such as mindfulness. They are framed like a game for engagement, where the subject can “get a power up” when they take 30 seconds to breathe deeply and think of 3 loved ones, as an example. 1 full daily activity is constituted by 4 to 6 very brief activities similar to the previously described.

Both groups will undergo physical exams at their normally scheduled orthopedic appointments at baseline, 8 weeks, 3 months, 6 months, 12 months, 18 months, and 24 months where presence/absence of reinjury, return to dance, adherence to PT and/or the SuperBetter app, type(s) of dance, and hours of dance per week will be assessed. Both groups will be asked to complete the PROMIS, SCS, and FAAM at baseline, 3-, 6-, 12-, 18-, and 24 months.

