8.2 SAFETY AND OTHER ASSESSMENTS

Subjects will be assigned exercises within the app by the “host,” which will be managed by the study staff. One activity will be released per day. They will only be sent 5 per week. To mitigate any potential fatigue, discomfort, or distress from the app usage, or questionnaires, we will inform participants that they may leave any survey question blank that they do not wish to answer, and to communicate with us should they feel they need to stop using the app at any time.

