9 STATISTICAL CONSIDERATIONS

9.1 STATISTICAL HYPOTHESES

- Primary Efficacy Endpoint(s):
 - Null Hypothesis (H_0): There will be no difference in self compassion scores to return to unrestricted dance at 3 months between the mental health app group and control group.
 - Alternative Hypothesis (H_1): Self compassion and return to unrestricted dance is expected to be improved in the mental health app treatment group compared to control group.
 - Type of Comparison: Superiority
 - Time Point: 12 months
 - Analysis Method: Logistic regression or Fisher's exact test depending on data distribution.
- Secondary Efficacy Endpoint(s):
 - Change in Self-Compassion Scale scores over time (repeated measures ANOVA or nonparametric equivalent) in experimental group compared to control group
 - Association of self-compassion with FAAM and PROMIS scores (correlation/regression)
 - Time to initial return to dance (Kaplan-Meier with log-rank test or Cox regression)
 - Reinjury incidence (descriptive comparison by self-compassion group)

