9.4.3 ANALYSIS OF THE SECONDARY ENDPOINT(S)

- Our secondary outcomes of interest are self-compassion scale (continuous), FAAM (continuous), PROMIS (continuous).
- Normally distributed data will be evaluated with ANOVA. Nonparametric data will be evaluated with the Mann-Whitney U.
- Subjects will be excluded from analysis if they are missing secondary outcomes of interest.

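### Participants may leave any questionnaire item blank, but section 9.4.3 answers a missing secondary outcome only by excluding the subject, which can discard nearly complete and possibly informative data

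*Protocol*

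**What the plan says.** Blank items are permitted in two places. Protocol section 2.3.1 observes that "broadly being asked about feelings such as depression and compassion for oneself may feel uncomfortable for some" and responds that "we will verbalize during enrollment that subjects may skip any questions they wish should any make them feel uncomfortable". Section 8.2, which also mentions fatigue, says "we will inform participants that they may leave any survey question blank that they do not wish to answer" and ties this to no particular kind of question.

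Section 9.4.3 names the SCS, FAAM and PROMIS scores as continuous secondary outcomes and states: "Subjects will be excluded from analysis if they are missing secondary outcomes of interest". It does not define when a score counts as missing, or whether the subject leaves one scale's analysis or all of them.

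Section 6.1.1 sets six questionnaire occasions: "Both groups will be asked to complete the PROMIS, SCS, and FAAM at baseline, 3-, 6-, 12-, 18-, and 24 months". Section 9.1 plans repeated measures ANOVA, or a nonparametric counterpart, for change in SCS. The protocol contains no scoring rule for partly answered forms and no imputation. Section 9.2 points to sensitivity analyses in 9.4.2 and 9.4.3 for missing primary data, but neither section contains one.

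**The concern.** One part of the protocol invites blanks inside returned forms. Another fixes a subject-level penalty for a missing outcome. Nothing in between says how a form with a blank is scored. If a blank leaves the scale without a score, a dancer who answered all other items is treated like one who answered none.

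Two things are at stake for the secondary endpoints.

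- **Lost data.** A trial of 50 has few subjects to spare, and most of the discarded answers exist. Under classical repeated measures ANOVA, which needs a score at every visit, one unscorable form can drop the dancer from the whole longitudinal comparison.
- **Selection.** Section 2.3.1 gives discomfort with questions on depression and self-compassion as a reason to skip. For SCS and PROMIS mental health, being excluded may therefore depend on the score itself.

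Self-compassion is the first secondary objective and appears in the stated hypotheses, so this is not a peripheral measure.

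**Working it through.** The protocol states no figure to reproduce. It gives neither item counts nor blank rates, so everything numerical below is illustration on stated assumptions.

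**Inputs from the protocol:** 50 enrolled (section 9.2); six questionnaire occasions (section 6.1.1).

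**Assumed:** k = 12 items for the SCS short form (10 to 30 as a range over scales); blank probability q per item of 0.5%, 1% or 2%; blanks independent; one blank makes the score missing.

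**1. Forms with at least one blank, 1 − (1 − q)^k**

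| k | q = 0.5% | q = 1% | q = 2% |
|---|---|---|---|
| 10 | 4.9% | 9.6% | 18.3% |
| 12 | 5.8% | 11.4% | 21.5% |
| 30 | 14.0% | 26.0% | 45.5% |

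For k = 12 and q = 1%: 1 − 0.99^12 = 1 − 0.886 = 0.114, leaving about 44 of 50 at one visit.

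**2. All six forms free of blanks, (1 − q)^(6k), k = 12**

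0.995^72 = 0.697, 0.99^72 = 0.485, 0.98^72 = 0.233, or about 35, 24 and 12 of 50. These apply only if the analysis requires a score at all six occasions. Blanks that cluster within persons give smaller losses.

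**3. Precision at one visit**

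The difference in means detectable with 80% power at two-sided 5% is about (1.960 + 0.842) × √(2/n) SD. With n = 25 per arm it is 2.802 × √(2/25) = 0.792 SD. With n = 22 (44 of 50 remaining) it is 2.802 × √(2/22) = 0.845 SD.

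**4. Shift of the analysed mean if skipping is related to the score**

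This is a different model from steps 1 and 2, since independent random blanks cause loss but no bias. Take self-compassion as standard normal; the lowest fifth has mean −1.40. If a fraction s of that fifth skips an item and is excluded, the excluded share is e = 0.20 × s and the remaining mean is e × 1.40 / (1 − e).

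- s = 25%: 0.05 × 1.40 / 0.95 = 0.07 SD
- s = 50%: 0.10 × 1.40 / 0.90 = 0.16 SD
- s = 75%: 0.15 × 1.40 / 0.85 = 0.25 SD

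A smoother model, simulated with the odds of skipping multiplied by e for each SD of lower self-compassion, gives about 0.09, 0.17 and 0.25 SD when 10%, 20% and 30% are excluded. If skipping is unrelated to the score, the shift is zero.

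**5. From a shifted mean to an arm difference**

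The same skipping pattern in both arms shifts both means alike and largely cancels in the contrast. A spurious difference of 0.16 SD requires half of the lowest fifth to skip in one arm and nobody in the other.

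**The case against.** The strongest reply is that section 9.4.3 speaks of missing outcomes, not missing items. Scoring of part-completed questionnaires is commonly left to the statistical analysis plan, which is not at hand. If an instrument's own rule yields a score despite a blank, the exclusion is never triggered. This stands: the loss is conditional. It does not remove the point, because the protocol itself fixes what happens when a score is missing, and it fixes it at subject level. A scoring rule elsewhere would reduce the unscorable forms but leave that consequence in place for the rest.

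A reader might infer more than the documents support:

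- **That any blank will exclude the dancer.** The protocol does not say so.
- **That precisely the distressed dancers are lost.** Only section 2.3.1 links skipping to discomfort, and it calls emotional discomfort unlikely and also lists boredom and fatigue. Section 8.2 allows blanks for any reason. FAAM asks about physical tasks, so this mechanism hardly reaches it.
- **That the arm comparison is biased.** The trial is unblinded and only one arm does mental health exercises, so different skipping is possible, but no passage shows it or its direction. Of the six forms, baseline precedes app use and those from 6 months onward follow its 12 weeks.
- **That half or more of the sample will be lost.** The six-visit figures need independent blanks and a complete-case longitudinal analysis. If distress drives skipping, blanks cluster and the losses are smaller.

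It is also fair to say that averaging the answered items is not neutral if the most distressing ones are those skipped.

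**Conclusion.** The point holds in conditional form and is worth a change before analysis. The protocol invites blanks and pairs them with subject-level exclusion as its only stated remedy for a missing secondary outcome. Where a blank leaves a scale unscored, usable answers are discarded, and for SCS and PROMIS mental health the discarding may depend on the construct.

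On the 12-item assumption with independent blanks, 6% to 22% of single-visit forms are at risk. The illustrative upward shift in the analysed mean is about 0.16 SD (0.07 to 0.25 SD over the range tried). That is modest beside the roughly 0.8 SD detectable with 25 per arm, and it becomes an arm difference only with differential skipping. Return to dance is recorded at clinic visits and does not depend on these scores.

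**What to change.** Keep the permission to skip, and replace the exclusion sentence in section 9.4.3 with the following:

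1. Score a partly answered form by the instrument's published rule or, where none exists, by a proration threshold fixed in advance.
2. If the form remains unscorable, set only that scale at that visit to missing and keep the subject's other data.
3. Analyse SCS over time with a method that uses all available visits, for example a mixed model for repeated measures, and amend section 9.1 to match. Without this step, classical repeated measures ANOVA would still drop the dancer.
4. Report the number of partly answered and unscorable forms by arm and visit, so that differential skipping can be seen.

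The cost is a few sentences, a scoring step and one change of model, with no change to data collection. The downside is some measurement error in prorated scores and possible residual bias if the most distressing items are the ones left blank.

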2.3.2 KNOWN POTENTIAL BENEFITS

Use of the SuperBetter app offers mental health benefits using a gamification design which has been shown to be an effective mental health intervention and also allows asynchronous intervention, preventing missed school and extra medical visits that would be required for virtual or in-person mental

health interventions (5). As such, use of the app may serve as a tool within the ongoing shortage of mental health resources.

2.3.3 ASSESSMENT OF POTENTIAL RISKS AND BENEFITS

Many older children/adolescents are using technology (computers, smart phones, tablets) for school and personal reasons, therefore the investigators do not feel use of this app would add significantly to the overall screen time for each individual patient, therefore the theoretical risks to the patient are low and the potential benefit high.

Numerous studies have investigated mental health in athletics, yet mental health in dancers is understudied. We believe through utilizing minimal-risk questionnaires about mental health and physical function, as well as implementing this mental health intervention, may help shed light on an important knowledge gap for this population and their recovery from injuries, including return to dance.

3 OBJECTIVES AND ENDPOINTS

OBJECTIVES	ENDPOINTS	JUSTIFICATION FOR ENDPOINTS
Primary		
To assess rates of return to dance without limitations after start of non-operative treatment in dancers recovering from foot and ankle injuries	Return to dance after treatment of injury	Investigators want to see the immediate effect of the mental health app on short-term recovery and return to dance, but also the longer lasting effects (if present) after injury recovery.
Secondary		
To assess self-compassion in the recovering dancer during and after the nonoperative treatment of their foot and ankle injury To assess musculoskeletal function during and after the recovery process	FAAM, PROMIS, and Self Compassion scores collected at 3, 6, 12, 18, and 24 months	Investigators want to see the immediate effect of the mental health app on short-term recovery and return to dance, but also the longer lasting effects (if present) after injury recovery.
Tertiary/Exploratory		
None		

4 STUDY DESIGN

4.1 OVERALL DESIGN

Null hypothesis (H_0): There will be no difference in self compassion scores to return to unrestricted dance at 3 months between the mental health app group and control group.

Alternative hypothesis (H_1): Self compassion and return to unrestricted dance is expected to be improved in the mental health app treatment group compared to control group.

Patient Enrollment and Randomization: Patients who meet inclusion criteria at this single site will be offered enrollment in this RCT. Enrolled patients will be randomized into one of 2 groups. It will be true randomization without patient preference but will not be blinded. There are no sub-studies or stratifications to be performed within this group.

Trial Interventions: Following randomization, the control group will undergo physical therapy treatment only while the experimental group will also participate in mental health exercises through the app, SuperBetter, for approximately 10 minutes 5 days per week for 12 weeks. All participants will have a minimum order of 8 weeks of physical therapy. At 8 weeks, depending on the individual patient and injury, the doctor may order an additional 4 weeks of PT, for a total of 12. This will be according to the physician's standard of care for their practice and clinical expertise. The number of PT visits ultimately attended by each subject will be recorded. If those in the treatment arm are not prescribed 4 additional weeks of PT at the 8-week time period, they will still use the app for 4 additional weeks for a total of 12 weeks of app usage.

Data collection: All patients in both groups will return to clinic at 3 months, 6 months, 12 months, 18 months, and 24 months. The 24-month visit represents completion of participation in the study. Throughout the trial, patients will be monitored for safe usage and engagement with the mobile app, to determine if they need to stop or limit the intervention.

4.2 SCIENTIFIC RATIONALE FOR STUDY DESIGN

The current study utilizes 2 groups, where one is treated with the intervention of the mental health app in addition to PT, and the other group only participates in SOC PT alone, as we are trying to see whether adding the mental health app component plays a role in improving rates of return to dance and recovery.

4.3 JUSTIFICATION FOR DOSE

Dosage of the SuperBetter mental health app will be 10 minutes, 5 days per week, for 12 weeks. The 10 minute length of the exercise is predetermined by the app. 5 days per week is the recommended frequency of app usage, which came from a 2021 study which showed 10 minutes per day, 5 days per week was effective to offer support to individuals with mild-to-moderate depression and anxiety symptoms, and be a possible, alternative solution for those who cannot attend in-person therapeutic sessions (22).

4.4 END OF STUDY DEFINITION

A participant is considered to have completed the study if he or she has completed all phases of the study including the last visit or the last scheduled procedure shown in the Schedule of Activities (SoA), Section 1.3.

The end of the study is defined as completion of the last visit or procedure shown in the SoA in the trial globally.

